7.2.1.2 Subject-Reported Heartburn Severity

For all the endpoints listed below, the mean value of dexlansoprazole capsules group was less than placebo group but the difference wasn't statistically significant (Table 15.2.5).

- The severity of daytime and nighttime heartburn over the 4 weeks of treatment as assessed by daily eDiary.
- The severity of nighttime heartburn over the 4 weeks of treatment as assessed by daily eDiary.
- The severity of daytime heartburn over the 4 weeks of treatment as assessed by daily eDiary.

7.2.2 Rescue Medication Use

For the percentage of days without rescue medication over 4 weeks, the mean value of dexlansoprazole capsules group (97.81%) was greater compared with placebo group (94.40%) and for the value reached 100%, the number of subjects in dexlansoprazole capsules group (84) was greater compared with placebo group (69). The distribution of the percentage of days without rescue medication use was statistically significant ($P=0.009$) (Table 15.2.4) different for the dexlansoprazole 30 mg QD and placebo.

7.3 Efficacy Conclusions

In this 4-week study comparing treatment with dexlansoprazole 30 mg QD or placebo in Chinese subjects with symptomatic nonerosive GERD, subjects treated with dexlansoprazole had a greater percentage of days with neither daytime nor nighttime heartburn and without nighttime heartburn than subjects taking placebo, but these differences were not statistically significant according to the pre-planned analysis.

Subjects in the dexlansoprazole treatment group with positive *H pylori* results or who were $\geq 90\%$ compliant with study drug did have a statistically significantly greater percentage of days without daytime and nighttime heartburn than those in the placebo group. Subjects in the dexlansoprazole treatment group also had statistically significantly greater reduction in severity of heartburn, acid regurgitation, and belching according to investigator assessment of symptoms after 4 weeks of treatment. In addition, subjects taking dexlansoprazole had a statistically

significantly greater percentage of days without rescue medication use over 4 weeks of treatment.

8.0 SAFETY EVALUATION

All the safety data were summarized in the safety analysis set.

8.1 Adverse Events

Similar percentages of subjects experienced at least 1 TEAE in the placebo and dexlansoprazole groups (32.4% and 36.4%, respectively) (Table 8.a). The majority of TEAEs in both groups were mild in severity and were not related to study drug.

No subjects died during the study (Appendix 16.2.7.4). One subject in the dexlansoprazole group experienced an SAE; the event was not related to study drug and did not lead to premature discontinuation (Appendix 16.2.7.3). Two subjects in each treatment group prematurely discontinued the study due to adverse events, the majority of which recovered and resolved (Appendix 16.2.7.2).

Table 8.a Overview of Treatment-Emergent AEs (Safety Analysis Set)

Category	Placebo QD N=108		Dexlansoprazole 30 mg QD N=107	
	Events	Subjects n (%)	Events	Subjects n (%)
Treatment-Emergent adverse event (TEAE)	70	35 (32.4)	63	39 (36.4)
Mild	61	27 (25.0)	47	26 (24.3)
Moderate	7	6 (5.6)	13	10 (9.3)
Severe	2	2 (1.9)	3	3 (2.8)
Related	21	13 (12.0)	24	15 (14.0)
Not Related	49	22 (20.4)	39	24 (22.4)
Leading to Study Drug Discontinuation	3	2 (1.9)	5	2 (1.9)
Serious adverse event (SAE)	0	0	1	1 (<1)
Related	0	0	0	0
Not Related	0	0	1	1 (<1)
Leading to Study Drug Discontinuation	0	0	0	0
Deaths	0	0	0	0

Source: Table 15.3.1.1.

8.1.1 Display of Adverse Events

All TEAEs are listed by subject in Appendix 16.2.7.1. Overall, the most frequently reported TEAEs occurring in $\geq 5\%$ of subjects in either treatment group (by MedDRA PT) were upper respiratory tract infection and nasopharyngitis (Table 8.b). All of these were non-serious adverse events that were not considered by the investigator to be related to study drug, and none led to study drug discontinuation.

Table 8.b Most Frequent Treatment-Emergent Adverse Events by Preferred Term - PT Occurring in $\geq 5\%$ of Subjects in Either Treatment Group (Safety Analysis Set)

PT	No. of Subjects (%)	
	Placebo QD N=108	Dexlansoprazole 30 mg QD N=107
Subjects with any TEAEs	35 (32.4)	39 (36.4)
Upper respiratory tract infection	8 (7.4)	5 (4.7)
Nasopharyngitis	7 (6.5)	4 (3.7)

Source: Table 15.3.1.7.1.

8.1.2 Deaths, Other Serious Adverse Events, and Other Significant Adverse Events

8.1.2.1 Deaths

No death was reported.

8.2 Clinical Laboratory Evaluation

8.2.1 Hematology

By-subject hematology parameters result are presented in Appendix 16.2.8.1.1 and the out-of-normal-range results are presented in Appendix 16.2.8.1.5.

Descriptive statistics for baseline, post baseline, and change from baseline to post baseline values for relevant hematology parameters are summarized in Table 15.3.4.1.3. Mean changes from baseline in hematology parameters in both groups were small and were not clinically concerning.

Some shifts from baseline to week 4 in hematology values were observed in both treatment groups and are summarized in Table 15.3.4.1.5. These shifts occurred in few subjects overall, and none were clinically concerning.

Hematology MAVs are summarized in Table 15.3.4.1.7.1 and listed in Appendix 16.2.8.1.8. No subjects in the dexlansoprazole group had hematology MAVs during treatment. Two subjects in the placebo group had hematology MAVs at week 4. One subject had markedly abnormally low hemoglobin (<88g/L). The second subject had markedly abnormally low platelets (<75×10³/μL). The hematology MAVs were not reported as AEs.

No subject had abnormalities in hematology parameters that were classified as SAEs.

8.2.2 Serum Chemistry

By-subject serum chemistry parameters results are presented in Appendix 16.2.8.1.2 and the out-of-normal-range result was presented in Appendix 16.2.8.1.6.

Descriptive statistics for baseline, post baseline, and change from baseline to post baseline values for relevant serum chemistry parameters are summarized in Table 15.3.4.1.4. Mean changes from baseline in chemistry parameters in both groups were small and were not clinically concerning.

Some shifts from baseline to week 4 in chemistry values were observed in both treatment groups and are summarized in Table 15.3.4.1.6. These shifts occurred in few subjects overall, and none were clinically concerning.

Chemistry MAVs are summarized in Table 15.3.4.1.7.1 and listed in Appendix 16.2.8.1.8. Two subjects (1 in each group) had a chemistry MAV during treatment. None of the MAVs were reported as an AE and none were clinically concerning.

8.2.3 Urinalysis

By-subject urinalysis results are presented in Appendix 16.2.8.1.3 and the out-of-normal range results are presented in Appendix 16.2.8.1.7. None of the urinalysis results were clinically concerning.

8.2.4 Serum Gastrin

The percentages of subjects with elevated gastrin values ≥200 pg/mL and ≥400 pg/mL are presented in Table 8.c. The number and the percentage of subjects with elevated gastrin values was greater in the dexlansoprazole capsules group than in the placebo group at week 4.

Descriptive statistics for baseline, post baseline, and change from baseline to post baseline values for gastrin are summarized in Table 15.3.4.1.10. The mean change value in the dexlansoprazole capsules group (73.9 pg/mL) were greater than those in the placebo group (-3.8 pg/mL) at week 4.

Table 8.c Summary of Gastrin Results (Safety Analysis Set)

	No. of Subjects (%)	
	Placebo QD N=108	Dexlansoprazole 30 mg QD N=107
Elevated Gastrin Values		
No. of Subjects at Visit 4 (Week 4)	102	103
≥200 pg/mL	6 (5.9)	15 (14.6)
≥400 pg/mL	3 (2.9)	4 (3.9)

Source: Table 15.3.4.1.8.

8.3 Vital Signs

By-subject vital signs data are presented in Appendix 16.2.8.2.1. Details of vital signs MAVs are summarized in Table 15.3.4.2.3.2 and listed in Appendix 16.2.8.2.2.

The descriptive statistics for baseline, post baseline, and change from baseline to post baseline values for vital signs are summarized in Table 15.3.4.2.2. The mean changes from baseline to week 4 in each group were small and not clinically concerning.

None of the vital signs MAVs were reported as an AE and none were clinically concerning.

8.4 12-Lead ECGs

By-subject ECG results are presented in Appendix 16.2.8.3.1. The descriptive statistics for baseline, post baseline, and change from baseline to post baseline ECG results are summarized in Table 15.3.4.3.2.

ECG MAVs are summarized in Table 15.3.4.3.3 and are listed by subject in Appendix 16.2.8.3.2. None of the ECG MAVs were reported as an AE and none were clinically concerning.

Shifts in ECG interpretation results are summarized in Table 15.3.4.3.4 and none were clinically concerning.

8.5 Other Observations Related to Safety

Physical examination results are presented in Appendix 16.2.8.4.

8.6 Safety Conclusions

In this 4-week study in Chinese subjects with symptomatic non-erosive GERD, treatment with dexlansoprazole 30 mg QD was generally well tolerated. The incidence of TEAEs was similar between subjects taking placebo or dexlansoprazole; most events were mild in intensity and were considered unrelated to treatment. The most frequently reported TEAEs were consistent with the known safety profile of dexlansoprazole. Few subjects experienced an AE that led to premature discontinuation. No study drug-related SAE was reported. There were no remarkable findings in the safety clinical laboratory, vital signs, or ECG data. Overall, no safety concerns were identified in this study.

9.0 DISCUSSION AND OVERALL CONCLUSIONS

9.1 Discussion

Phase 3 studies performed in the United States have demonstrated positive results using dexlansoprazole capsules for heartburn relief in subjects with symptomatic nonerosive GERD. This study was the first to examine the efficacy and safety of dexlansoprazole capsules in Chinese subjects with symptomatic nonerosive GERD.

The main objective of this phase 3, double-blind, randomized study was to compare the efficacy of dexlansoprazole capsule (30 mg QD) and placebo in relief of daytime and nighttime heartburn over 4 weeks in Chinese subjects with symptomatic nonerosive GERD as assessed by daily electronic diary (eDiary).

No major differences in subject disposition were observed across treatment groups. Subject discontinuation rates in dexlansoprazole capsules groups (3.7%) were generally lower than placebo group (5.5%). Treatment compliance was high in all groups, with $\geq 97\%$ of the total 215 subjects maintaining greater than 90% compliance with the dosing schedule. Similarly, no major differences were observed across treatment groups in subject demographics. More females (58.1%) were enrolled in the study (consistent across treatment groups); however, this gender difference did not have an impact on the analysis of efficacy results. Approximately 51% of subjects were aged from 45 to 65 years. A small proportion of subjects were aged 65 years or older (4.2%); therefore, any interpretation of efficacy results in these subjects is limited.

The results of Study TAK-390MR_302 showed that, although subjects in the dexlansoprazole group had a greater percentage of days with neither daytime nor nighttime heartburn than those taking placebo, the results of the primary endpoint (percentage of days and nights without heartburn) did not reach statistical significance based on the original planned analysis ($p=0.057$). Statistical significance was missed by a small margin. As an indication of how close the results were to reaching significance, when analyzed in subjects with the highest treatment compliance ($\geq 90\%$), the difference was statistically significant; these results indicate that dexlansoprazole treatment was more effective than placebo for treating Chinese subjects with symptomatic nonerosive GERD when the medication was taken consistently. Subjects who took dexlansoprazole also had a greater percentage of nights without heartburn than those who took placebo, but the difference was not statistically significant. Subjects in the dexlansoprazole group had statistically significantly greater reductions in investigator-assessed symptoms of heartburn, acid regurgitation, and belching after 4 weeks of treatment, and also used statistically significantly less rescue medication than subjects in the placebo group.

After the unblinded results for the primary and secondary endpoints were available, an *ad hoc* sensitivity analysis (two sample t-test) was performed to explore the influence of the higher than expected placebo response in light of the fact that the p-value for the primary analysis of the primary endpoint was insignificant by only a small amount. The sensitivity analysis results in a statistically significant difference between the group means for the primary endpoint (percentage of days with neither daytime nor nighttime heartburn, $p=0.029$). The difference between groups

for the secondary endpoint (percentage of days without nighttime heartburn) was not statistically significant based on the sensitivity analysis ($p=0.365$).

The results of Study TAK-390MR_302 were similar to Study T-GD05-137 (on which the assumptions for study power were based) for measuring the dexlansoprazole treatment effect, but were not consistent for measuring the placebo effect. Because this was a well-controlled clinical trial, a few of the reasons that might explain this outcome are discussed herein.

One possible reason for the outcome of this study is random chance. With a type 1 error rate of 5%, this study had a 1 in 20 chance of showing non-significant results when a true treatment difference existed. It is interesting to recall that in the dexlansoprazole pivotal trials, a stronger level of significance ($\alpha=0.0025$) was used and satisfied.

Another possible reason for the outcome may be that the placebo effect is higher among the population sampled in this study than the population sampled in previous dexlansoprazole studies. In this case, the situation is not that the active treatment is disproven as effective, but is that the study wasn't adequately powered to measure the treatment differences. The assumptions for which this study was powered (ie, sample size determination) were based on Study T-GD05-137, in which the mean percentage of days without daytime or nighttime heartburn for subjects taking placebo was 25%; this placebo response rate was similar in the other dexlansoprazole studies that included a placebo arm (Studies T-GD04-082 and T-GD07-170). High placebo response rates have been observed in other studies of symptomatic GERD [1-3]. Chinese subjects who took placebo in Study TAK-390MR_302, however, had a higher placebo response rate (mean percentage of days without daytime or nighttime heartburn was 37%).

A final reason for the outcome of Study TAK-390MR_302 may be that the disease burden of those sampled was not exactly comparable to that of the patients who participated in the US pivotal and supportive studies, which resulted in the higher than expected placebo response.

For at least two of the three possible reasons described here, the lack of statistical significance shown for the primary endpoint in Study TAK-390MR_302 is not because of a lack of treatment effect, but because the study was not adequately powered to detect the treatment differences. The result of the *ad hoc* sensitivity analysis supports this conclusion. The t-test used in the sensitivity analyses is a more statistically powerful test than the Wilcoxon rank sum test, when certain assumptions are met. In the case of a large sample size (eg. 200 subjects), the t-test is robust.

Although the placebo response rate observed in this study of Chinese subjects was unexpected based on previous dexlansoprazole data, it is not inconsistent with the results of a similar study in another Asian population. Specifically, Hongo, et al, studied the efficacy of famotidine (an H2RA) in Japanese patients with nonerosive reflux disease in a double-blind, placebo-controlled, parallel-group, multicenter study [4]. The percentage of days without heartburn over 8 weeks for subjects on active treatment in this study ranged between 59% and 62% depending on dose, while subjects who took placebo had a response rate of 55%. The authors who reported the results of this study concluded that "the efficacy of placebo is considerably higher in Japanese nonerosive GERD patients than in Western nonerosive GERD patients."

There may be several physiological reasons for the higher-than-expected placebo response rate observed in Chinese patients with symptomatic nonerosive GERD in Study TAK-390MR_302. Asian patients have lower gastric acid output than white patients [5], as well as lower rates of TLESR [6]; thus, Asian patients may experience fewer acid-related GERD symptoms than their western counterparts. It has also been suggested that factors other than acid may be important in the pathophysiology of nonerosive GERD in Chinese patients, such as esophageal hypersensitivity, weakly acid or weakly alkaline reflux, or psychosocial factors [7]. This hypothesis was based on the results of an esomeprazole study in Chinese patients with symptomatic nonerosive GERD, in which esomeprazole was effective in relieving symptoms, but a lower complete symptom response rate was observed than in studies of PPIs in Western patients with nonerosive GERD. It is important to keep in mind, however, that it is not possible to draw definitive conclusions about placebo response rates in Asian patients compared to their western counterparts based only on data from 2 relatively small studies in Chinese patients.

For the additional analyses, a statistically significant improvement in the days without rescue medication over 4 weeks was observed for dexlansoprazole capsules compared with placebo. For each GERD symptom, the mean severity scores decreased from baseline at weeks 2 and 4 for both placebo and dexlansoprazole groups. Reductions in severity for heartburn were significantly greater in the dexlansoprazole group than placebo for both Week 2 ($p=0.009$) and Week 4 ($p=0.005$). Reductions in severity for acid regurgitation and belching were significantly greater in the dexlansoprazole group than placebo at Week 4 ($p=0.008$ and $p=0.042$). There were no significant difference for dysphagia or epigastric pain.

The proportion of subjects with any TEAE was similar in the placebo and dexlansoprazole groups (32.4% and 36.4%, respectively). The proportion of subjects with a TEAE that led to study discontinuation was low, supporting that dexlansoprazole capsules were well tolerated by Chinese subjects. Only one SAE was observed, but it was not considered to be related to study drug. No deaths were reported during this study. There were no abnormalities that were classified as SAEs with respect to vital signs, ECG results, or laboratory parameters.

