5.9 Study Drug Exposure and Overdose

Overall study drug compliance (%) was determined as (total count of capsules taken / total number of days on study drug) \times 100%. The total number of days on study drug (exposure) was

calculated as date of last dose of study drug - date of first dose of study drug + 1, assuming no gaps in the dosing interval. Any gaps in dosing interval was ignored in the calculation of the total. If last dose date was missing, then 35 days were imputed as treatment period. Summary statistics for the total number of days on study drug and overall compliance were generated for the safety analysis set.

The number and percentage of subjects with overall study drug compliance of <80%, 80-<90%, and ≥90% was also summarized for the safety analysis set. Subjects with unreturned study drug were assumed to have taken 1 capsule of study drug for each day of exposure for the calculation of overall compliance. Subjects with overall compliance ≥100% were set to 100% in the analysis.

In addition, diary compliance was determined as the percentage of days during treatment with two diary entries:

$$\text{Diary Compliance} = \frac{\text{(Number of days with two diary entries collected during treatment period)}}{\text{(Number of days with two diary entries expected during treatment period)}} \times 100\%$$

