5.10.1 Primary Efficacy Endpoint

The percentage of days with neither daytime nor nighttime heartburn over the 4 weeks of treatment was summarized descriptively. Comparisons between dexlansoprazole capsules and placebo was made using a Wilcoxon rank-sum test. The two-sided p-value was presented for the difference between dexlansoprazole capsules and placebo; the difference was considered statistically significant if the p-value was less than 0.05.

The percentage of days with neither daytime nor nighttime heartburn was calculated for each subject who has at least 1 daytime or nighttime heartburn result (presence or absence of heartburn) during the 4 weeks of treatment (up to last dose day or Day 35 whichever is first) by calculating:

$$\text{Percentage of days with neither daytime nor nighttime heartburn} = \frac{\text{(the days that were heartburn-free during Treatment Period)}}{\text{(Total number of days for which either a daytime or nighttime result was marked during Treatment Period)}} \times 100\%;$$

all entries on a day must be heartburn-free in order for the day to be counted as a day with neither daytime nor nighttime heartburn.

The days with missing diary results for both daytime and nighttime were excluded from the numerator and denominator. If a subject prematurely terminated, the Treatment Period was defined as from first dose date to last dose date + 1 day. If last dose date was missing, then 35 days was imputed as treatment period.

Subgroup Analyses:

Similar descriptive statistics and Wilcoxon rank-sum tests were repeated on the primary endpoint to evaluate the treatment effect within the different baseline subpopulation levels as follows:

- Age (<45, ≥45 to <65, ≥65 years).
- Gender (male, female).
- BMI (<25, 25-<30, ≥30 kg/m²).
- *H pylori* status (positive, negative).
- Overall study drug compliance (<80%, 80-<90%, ≥90%).

Ad Hoc Sensitivity Analysis

Similar descriptive statistics and two sample T-test were repeated on the primary endpoint to evaluate the treatment effect.

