7.1 Primary and Secondary Efficacy Endpoint

The median percentage of days with neither daytime nor nighttime heartburn for subjects in the dexlansoprazole capsules group (51.72%) was greater than for subjects in the placebo group (32.67%) with the difference of 19.05%. The difference between treatment groups was not statistically significant ($P=0.057$) (Table 7.a).

Subgroup analyses were performed on the primary endpoint, and these results are presented in Table 7.b. For subjects with positive *H pylori* results, the median percentage of days with neither daytime nor nighttime heartburn for subjects in the dexlansoprazole capsules group (68.62%) was greater than for those in the placebo group (34.62%), and the difference (34.00%) was statistically significant with $p\text{-value} = 0.032$. For subjects with the highest overall study drug compliance ($\geq 90\%$), the median in the dexlansoprazole capsules group (51.72%) was also greater than for those in the placebo group (30.29%), and the difference (21.43%) was statistically significant with $p\text{-value} = 0.037$.

For the secondary endpoint of percentage of days without nighttime heartburn over 4 weeks, the median value of dexlansoprazole capsules group (67.86%) was greater compared with placebo group (54.67%). The difference (13.19%) between treatment groups was not statistically significant ($P=0.268$) (Table 7.a).

For the percentage of days without daytime heartburn over 4 weeks, the median value of dexlansoprazole capsules group (62.96%) was greater compared with placebo group (46.55%) (Table 7.a).

An ad hoc sensitivity analysis was performed on the primary and secondary efficacy endpoints.. For primary efficacy endpoint, the difference between treatment groups was statistically significant ($P=0.029$) (Table 15.2.6). For the secondary efficacy endpoint, the difference between the treatment groups was not statistically significant ($P=0.365$) (Table 15.2.7).

Table 7.a Percentage of Days Without Heartburn During Treatment (Full Analysis Set)

	Placebo QD N = 108	Dexlansoprazole 30 mg QD N = 107
Primary endpoint: percentage of days with neither daytime nor nighttime heartburn during treatment ^a		
N	108	107
Mean (SD)	36.98 (31.999)	47.21 (35.995)
Median	32.67	51.72
P-value ^b		0.057
Secondary endpoint: percentage of days without nighttime heartburn during treatment		
N	108	107
Mean (SD)	50.38 (34.309)	54.83 (37.449)
Median	54.67	67.86
P-value ^b		0.268

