Additional endpoint: percentage of days without daytime heartburn during treatment		
N	108	107
Median	46.55	62.96

Source: [Table 15.2.1](#).

QD: once daily.

^a Percentage of days with neither daytime nor nighttime heartburn = (the days that are heartburn-free during treatment period) / (total number of days for which either a daytime or nighttime result is marked during treatment period) × 100%.

^b The 2-sided p-value was obtained using the Wilcoxon rank-sum test.

Table 7.b Subgroup Analyses of Percentage of Days With Neither Daytime Nor Nighttime Heartburn Over 4 Weeks (Full Analysis Set)

	Placebo QD N=108	Dexlansoprazole 30 mg QD N=107
Age (<45 years)		
N	46	50
Mean (SD)	39.40 (34.297)	53.09 (34.458)
P-value		0.068
Age (≥45 to 65 years)		
N	57	53
Mean (SD)	35.02 (29.633)	41.79 (36.018)
P-value		0.472
Age (≥65 years)		
N	5	4
Mean (SD)	37.17 (41.722)	45.37 (52.932)
P-value		0.898
Gender (Male)		
N	43	47
Mean (SD)	34.40 (33.307)	49.51 (37.033)
P-value		0.063
Gender (Female)		
N	65	60
Mean (SD)	38.70 (31.248)	45.40 (35.370)
P-value		0.381
BMI (<25 kg/m²)		
N	69	72
Mean (SD)	37.94 (31.249)	45.50 (36.638)
p-value		0.298
BMI (≥25 to 30 kg/m²)		
N	34	28
Mean (SD)	34.93 (33.229)	51.55 (36.338)
p-value		0.104
BMI (≥30 kg/m²)		
N	5	7
Mean (SD)	37.78 (40.352)	47.39 (30.665)
p-value		0.744

	Placebo QD N=108	Dexlansoprazole 30 mg QD N=107
H pylori status (positive)		
N	41	40
Mean (SD)	39.87 (30.941)	55.95 (35.893)
p-value		0.032
H pylori status (negative)		
N	67	67
Mean (SD)	35.22 (32.733)	41.99 (35.294)
p-value		0.403
Overall study drug compliance (<80%)		
N	0	1
Mean (SD)		0.00 (NA)
p-value		NA
Overall study drug compliance (80-<90%)		
N	1	3
Mean (SD)	83.33 (NA)	64.74 (37.701)
p-value		>0.999
Overall study drug compliance (≥90%)		
N	106	103
Mean (SD)	35.95 (31.370)	47.15 (35.884)
p-value		0.037

Source: Table 15.2.2.

Note 1: Percentage of days with neither daytime nor nighttime heartburn = (the days that are heartburn-free during Treatment Period)/(Total number of days for which either a daytime or nighttime result is marked during Treatment Period) * 100%.

Note 2: The p-value was obtained using the Wilcoxon rank-sum test.

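### A compliance subset defined after randomisation is labelled baseline and used to claim efficacy under consistent dosing, which the reported figures do not support

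*SAP*

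**What the plan says.** SAP 5.10.1 repeats the primary analysis by subgroup to "evaluate the treatment effect within the different baseline subpopulation levels as follows". The list is age, gender, BMI, H pylori status and overall study drug compliance (below 80%, 80 to below 90%, 90% or more). SAP 5.9 defines the last of these: "Overall study drug compliance (%) was determined as (total count of capsules taken / total number of days on study drug", where days on drug run from first to last dose. Unreturned drug is counted as taken.

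For the primary test, "the difference was considered statistically significant if the p-value was less than 0.05". SAP 7.1 reports p=0.057 in the full analysis set and p=0.037 in the subset with at least 90% compliance.

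SAP 7.3 says that dexlansoprazole subjects who were H pylori positive, or at least 90% "compliant with study drug did have a statistically significantly greater percentage of days without daytime and nighttime heartburn than those in the placebo group". SAP 9.1 goes further and says the compliance result indicates that "dexlansoprazole treatment was more effective than placebo for treating Chinese subjects with symptomatic nonerosive GERD when the medication was taken consistently". The same section puts at least 97% "of the total 215 subjects maintaining greater than 90% compliance with the dosing schedule".

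**The concern.** Compliance is known only after dosing, and it can depend on tolerability and response. Selecting on it breaks the randomised comparison, whatever the subgroup is called.

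The 9.1 sentence also makes consistent dosing the condition under which the drug works. If that were so, the active arm should do better among compliant subjects than in the full set. If it does not, the smaller p-value has another source.

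A reader of 7.3 and 9.1 could take the missed endpoint as an adherence problem, on the strength of a nominal p-value from a selected subset. Separately, 7.3 sets the H pylori-positive result (p=0.032) beside the compliance result without a test of whether the effect differs by H pylori status.

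**Working it through.** **Inputs** (SAP Tables 7.a and 7.b, percentage of days with neither daytime nor nighttime heartburn)

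| Set | Placebo n, mean (SD), median | Dexlansoprazole n, mean (SD), median |
|---|---|---|
| Full analysis set | 108, 36.98 (31.999), 32.67 | 107, 47.21 (35.995), 51.72 |
| Compliance ≥90% | 106, 35.95 (31.370), 30.29 | 103, 47.15 (35.884), 51.72 |
| 80 to <90% | 1, 83.33 | 3, 64.74 (37.701) |
| <80% | 0 | 1, 0.00 |

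The medians are from 7.1.

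**1. Reproduce a reported figure.** The Wilcoxon p-values need patient-level data. The ad hoc t-test can be rebuilt from the summaries. Pooled variance = (107×31.999² + 106×35.995²)/213 = 1159.2. SE = √[1159.2×(1/108 + 1/107)] = 4.64. t = 10.23/4.64 = 2.20, p=0.0287, against 0.029 reported.

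**2. Size of the subset.** (106+103)/215 = 97.2%, in line with the statement in 9.1.

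**3. Which arm moves.**
- Mean difference: 47.21−36.98 = 10.23 in the full set and 47.15−35.95 = 11.20 in the subset, a rise of 0.97.
- Placebo contributes 36.98−35.95 = +1.03; dexlansoprazole contributes 47.15−47.21 = −0.06.
- Median difference: 51.72−32.67 = 19.05 becomes 51.72−30.29 = 21.43, all from placebo.

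**4. Who is left out.**
- Dexlansoprazole: four subjects, mean (0 + 3×64.74)/4 = 48.6, close to the 47.15 of those kept. Check: (0 + 3×64.74 + 103×47.15)/107 = 47.20, against 47.21 reported.
- Placebo: the compliance rows sum to 0+1+106 = 107. Age (46+57+5), gender (43+65), BMI (69+34+5) and H pylori (41+67) each sum to 108, so one placebo subject is in no compliance row.
- That subject's value from the means: 108×36.98 − 106×35.95 − 83.33 = 99.8. Rounding allows 98.7 to 100.9, so at most 100. From the SDs, with sum of squares = (n−1)SD² + n×mean², it is √9986.7 = 99.9.
- The two omitted placebo subjects therefore average (108×36.98 − 106×35.95)/2 = 91.6, against 35.95 for those kept.

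**5. Which omissions change the p-value.** t-tests from the summaries:

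| Comparison | Difference | p |
|---|---|---|
| Full set | 10.23 | 0.029 |
| Omit 4 dexlansoprazole only | 10.17 | 0.031 |
| Omit 2 placebo only | 11.26 | 0.016 |
| Omit all 6 | 11.20 | 0.017 |

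This shows which arm matters, but it is not the Wilcoxon test. As an illustration for that test, beta-distributed data matched to the subset means and SDs on a 28-day grid were kept when the full-set Wilcoxon p was 0.047 to 0.067 (300 runs). Mean p was 0.057 for the full set, 0.059 omitting the four dexlansoprazole subjects, 0.035 omitting the two placebo subjects and 0.037 omitting all six.

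**6. What the measure captures.** Ten subjects stopped drug early (SAP 6.1) but only 215−209 = 6 fall outside the ≥90% row. At least 4 early stoppers therefore count as highly compliant, because the denominator ends at each subject's own last dose.

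**7. Baseline subgroups.** For H pylori, the effect is 55.95−39.87 = 16.08 (SE 7.45) in positives and 41.99−35.22 = 6.77 (SE 5.88) in negatives. The difference is 9.31, SE √(7.45²+5.88²) = 9.49, z=0.98, p=0.33, 95% CI −9.3 to 27.9. The same inverse-variance heterogeneity approach gives p=0.76 for age (Q=0.54, 2 df), 0.38 for gender (Q=0.78, 1 df) and 0.69 for BMI (Q=0.73, 2 df).

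**The case against.** The missed primary endpoint is reported honestly in the synopsis, 7.1, 7.3, 9.1 and 9.2, and neither the synopsis nor 9.2 uses the compliance subset. SAP 9.1 introduces the result as a sign of how close the trial came, and its listed explanations are chance, placebo response and disease burden, not adherence. The compliance subgroup is absent from the post-unblinding changes in 5.15, so nothing visible shows it was post hoc. The 7.3 sentence restates a tabulated result correctly. Dropping 4 of 107 active subjects could hardly move that arm's mean. H pylori is a separate matter, and 7.3 claims no differential effect.

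Most of this is true and limits the reach of the problem. It does not rescue the 9.1 sentence, which goes from closeness to significance to a statement about efficacy under consistent dosing. That the active mean could hardly move is itself the reason the subset cannot support such a statement. The point on 7.3 supports qualifying the sentence as an alternative to deleting it.

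Two cautions also stand. The Wilcoxon p=0.037 has not been shown to be wrong, and its cause is inferred. The unclassified placebo subject may be explained in source tables or file notes that were not available.

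**Conclusion.** The concern holds. Compliance is a post-randomisation variable wrongly described as baseline, and the inference in 9.1 fails on the published means and medians alone, with no distributional assumption. The active arm is unchanged in the subset, and the 0.97-point gain in mean difference comes entirely from omitting two placebo subjects with about 83% and 100% heartburn-free days.

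That these two omissions also explain the fall in the Wilcoxon p-value from 0.057 to 0.037 is very likely, but needs patient-level data to confirm. With one placebo and four active subjects classified below 90%, the trial can say almost nothing about adherence and effect.

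The interaction p-values (0.33 to 0.76) are approximations from summary statistics, and the oldest age and highest BMI strata are very small. They give no evidence that the effect varies by any baseline factor, including H pylori. The reported primary result and the conclusion in 9.2 are unaffected.

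**What to change.** - **SAP 5.10.1:** take compliance out of the baseline subgroup list, or label it a descriptive subset defined after randomisation.
- **SAP 9.1:** delete the conclusion about efficacy under consistent dosing.
- **SAP 7.3:** delete the claim for the ≥90% subset. If the subset is kept, qualify it along these lines: *In the subset with at least 90% compliance (209 of 215 subjects), which is defined after randomisation, the dexlansoprazole result was unchanged from the full analysis set; this subset gives no evidence on the effect of consistent dosing.*
- **Table 7.b:** add a footnote accounting for the placebo subject who is in no compliance row.
- **Baseline subgroups:** report treatment-by-subgroup interaction tests for age, gender, BMI and H pylori. If the patient-level tests agree with the approximations here, state that there is no evidence that the effect differs by H pylori status.

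The cost is wording in three sections, one footnote and four tests on existing data.
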